2.0 Objectives

2.1 The purpose of this study is to examine interest in receiving contraception counseling and contraception initiation female adolescents hospitalized with mental health disorders.

The primary objectives of this study are to 1) Examine interest in receiving contraception counseling among female adolescents hospitalized with mental health disorders, and 2) Examine contraception initiation among female adolescents hospitalized with mental health disorders.

Multiple secondary objectives will be investigated during the study. They include:

- To assess the proportion of female adolescents hospitalized with mental health disorders that receive contraception counseling or are prescribed/initiate any contraceptive during hospital admission or immediately post discharge.

- To determine predictors of receipt of contraception counseling and contraception initiation among female adolescents hospitalized with mental health disorders
- Assess satisfaction with and person-centeredness of contraception care among participants who received contraceptive counseling

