6.0 Procedures Involved*

6.1 This is an observational study. The study components include participant surveys, EHR data extracts related to sexual and reproductive health, and statistical process control charts for quality improvement analyses. Three surveys will be administered to participants, the first at the time of enrollment, the second immediately after discharge, and the third four months after discharge.

6.2 Potential participants will be approached during their admission at NCH and invited to participate in the study. If they are interested in participation, they will complete an electronic informed consent via redcap, all study participants will receive a copy of their consent via e-mail. If the participant is 14 years old the coordinator will be required to obtain verbal consent from the parent or guardian via Information Sheet. After the consent process is completed, they will fill out the first study survey while they are admitted to the hospital (see Appendix A). The

PROTOCOL TITLE: Evaluation of Contraception Care @ Behavioral Health Pavilion

subsequent two surveys will be sent electronically via their preferred communication method, which will be determined at enrollment. After the last survey is completed the subject will have completed their portion of the study. This is a study with adolescents as the study population and there will be little parental involvement, there are concerns regarding study retention. We will be providing texts as a communication option for the participants as we believe this will be most successful. If a participant chooses this as their preferred contact method. In order to text participants, we will be utilizing Twilio, an NCH approved application.

Study staff will review responses on the following questions on the baseline survey: if the participant indicates they would like to a) learn more about, b) initiate or change contraception methods, and c) desire for privacy for contraception care. Study staff will notify the patient's clinical team if any of these are positive.

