10.0 Inclusion and Exclusion Criteria*

10.1 The study coordinator will screen for eligible patients each morning by checking the census in the EHR of specified behavioral health units. The coordinator will enter the charts of patients that appear to be eligible for the study to determine whether they meet inclusion criteria.

10.2 Inclusion criteria: female adolescents, 14 years and older, admission to the following units – Psychiatric Units (BHP7B and 8A), Youth Crisis Stabilization Unit, Psychiatric Crisis Department Extended Observation Care Unit and patients with mental health disorders admitted to Hospital Pediatrics 3 service awaiting a psychiatric bed/disposition.

Exclusion criteria: wards of state, unable to consent due to mental health disorder, serious medical conditions, non-English speaking, intellectual disability, and known pregnancy.

10.3 Indicate specifically whether you will include or exclude each of the following special populations:

- Individuals who have not yet reached the age of legal consent will be required to complete study consent. We will be submitting the form to waive parental consent for participants 15 and older as the study questions are sensitive and may impede ability to enroll participants with requirements for parental consent. We will require verbal, parental consent for potential participants who are 14 years of age. We will provide the parent or guardian with a study Information Sheet.
- Pregnant women will be excluded from eligibility in the study. However, if a participant becomes pregnant during the study she will not be required to withdraw, as the only study procedures are questionnaires.

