17.0 Data Management* and Confidentiality

17.1 *Describe the data analysis plan, including any statistical procedures or power analysis.*

For our first objective, the dependent variables are interest in receiving contraception counseling during a hospital stay and interest in starting a contraceptive during a hospital stay.

- We will examine interest in receiving contraception counseling during hospitalization among female adolescents hospitalized with mental health disorders by assessing the proportion of participants who answer yes to the following survey question “Interest in learning more about contraception during your hospital stay”.
- We will examine interest in initiating contraception during hospitalization among female adolescents hospitalized with mental disorders by assessing the proportion of participants who answer yes to the following question “Interest in starting a contraceptive during your hospital stay”.
- We will perform univariate descriptive analyses on all variables.
- We will perform bivariate analysis to explore the relationship between variables “Interest in learning more about contraception during your hospital stay” and “Interest in starting a contraceptive during your hospital stay” using 2 X 2 contingency tables.

PROTOCOL TITLE: Evaluation of Contraception Care @ Behavioral Health Pavilion

- We will explore associations with dependent variables and predictor variables by performing bivariate analyses of “Interest in learning more about contraception during your hospital stay” and “Interest in starting a contraceptive during your hospital stay” with predictor variables from surveys and EHR variables using Chi square for categorical variables and Students T-test for continuous variables.
- We will regress significant predictor variables ($p < 0.1$) on dependent variables to determine predictors of “interest in receiving contraception counseling during your hospital stay” and “interest in starting a contraceptive during your hospital stay”.

For our second objective the dependent variables are contraceptive prescription/initiation during hospitalization and contraceptive prescription/initiation following discharge.

- We will create derived variables:
 - Initiation any contraceptive (in hospital, in BC4Teens clinic, none)
 - Initiation preferred contraceptive (in hospital, in BC4Teens clinic, none)
 - Time interval (days) between enrollment and contraception prescription/initiation

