 - Initiation of contraceptive not preferred contraceptive (in hospital, in BC4Teens)
- We will perform univariate descriptive analyses on all variables.
- We will examine contraception initiation all among participants by assessing the proportion of participants who initiate any contraceptive in the a) hospital setting, b) in BC4Teens clinic, and c) either hospital or BC4Teens clinic.
- We will examine contraception initiation all among participants by assessing the proportion of participants interested in contraception care who initiate any contraceptive in the a) hospital setting, b) in BC4Teens clinic, and c) either hospital or BC4Teens clinic.
- We will examine how time between enrollment and Initiation any contraceptive varies by location of contraception prescribing/initiation using Student’s T test.
- We will also perform the 3 analyses above on the variable “initiate preferred contraceptive”
- We will examine the type of contraceptive method prescribed/initiated in the a) hospital setting, b) in the BC4Teens clinic setting, and c) either hospital or BC4Teens clinic
- We will examine variation in type of contraceptive method prescribed/initiated between the hospital setting and the BC4Teens clinic setting using Chi square.
- We will explore associations with dependent variables and predictor variables by performing bivariate analyses of “initiation

PROTOCOL TITLE: Evaluation of Contraception Care @ Behavioral Health Pavilion

any contraceptive” and predictor variables from surveys and EHR variables using Chi square for categorical variables and Students T-test for continuous variables.

- We will regress significant predictor variables ($p < 0.1$) on dependent variables to determine predictors of initiation any contraceptive.
- To better understand personal and system-level differences in initiation of contraception during hospitalization and in BC4Teens clinic, we will examine differences in demographics, survey variables of interest, and EHR variables of interest between participants who initiate “any contraceptive during hospitalization” and initiate “any contraceptive in BC4Teens clinic” using Chi square.

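### The predictor screen and regression for contraceptive initiation name no analysis population and take no account of contraceptive use at enrollment

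*Combined protocol and SAP*

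**What the plan says.** A secondary objective in section 2.1 is "To determine predictors of receipt of contraception counseling and contraception initiation among female adolescents hospitalized with mental health disorders". Section 17.1 gives the planned answer under the second objective:

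- **Outcome.** There, "the dependent variables are contraceptive prescription/initiation during hospitalization and contraceptive prescription/initiation following discharge". The derived variable has three levels: "Initiation any contraceptive (in hospital, in BC4Teens clinic, none"). No level or flag marks a participant already using a method.
- **Screen.** Initiation is tested against each candidate, "and predictor variables from surveys and EHR variables using Chi square for categorical variables" and t-tests for continuous ones.
- **Regression.** Variables with p<0.1 are regressed "on dependent variables to determine predictors of initiation any contraceptive".

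Neither the screen nor the regression names an analysis population, a stratum or a forced covariate. Earlier bullets in section 17.1 give initiation proportions among all participants and among those interested in contraception care. The second group is not defined by current use and is not carried into the predictor steps.

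Current users can enroll. Section 10.2 includes by sex, age and unit, and its exclusions do not mention contraceptive use: "Exclusion criteria: wards of state, unable to consent due to mental health disorder, serious medical conditions, non-English speaking, intellectual disability, and known pregnancy". Section 6.2 expects some users, because the baseline items that staff review include a wish to "b) initiate or change contraception methods".

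**The concern.** A participant already on a method is in a different position from one who is not. If she changes nothing, the derived variable appears to leave her only the third level, alongside a non-user who did not start. If she switches or renews, the joint prescription/initiation wording may count her with new starts. Two analysts could build different outcomes from the same text.

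This matters for the predictor steps because many plausible predictors may be related to existing use. A variable more common among current users can then look like a barrier to starting, or its real effect on starting can be masked. With use in the opposite pattern, a real effect is exaggerated. The p<0.1 screen comes first and is unadjusted, so a variable lost there never reaches the regression. At stake is whether the reported predictors describe who starts a method or partly describe who already had one.

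**Working it through.** **The plan's own figure.** Sections 12.1 and 12.2 give 1,000 eligible × 0.45 agreeing = 450, which reproduces. It is a recruitment estimate, not a power calculation. The documents give no prevalence of use, no expected initiation rate and no rate at which users would be counted. Every rate below is therefore an assumption.

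**Set-up.** Take a binary predictor splitting the sample 225/225, with the outcome collapsed to initiated or not. In each predictor group, u is the share of current users, p the share of non-users who start, and s the share of users counted as initiating (the same s in both groups).

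- Crude rate: r = (1 − u)p + u·s.
- With d = r1 − r0 and r̄ = (r1 + r0)/2: S0 = √[2r̄(1 − r̄)/225] and S1 = √[(r1(1 − r1) + r0(1 − r0))/225].
- Chance of p<0.1 = Φ[(d − 1.645·S0)/S1] + Φ[(−d − 1.645·S0)/S1].

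**Step 1: a real predictor.** p = 0.30 vs 0.15, s = 0. Worked case, use 40% vs 10%: r1 = 0.6 × 0.30 = 0.180 and r0 = 0.9 × 0.15 = 0.135, so d = 0.045, S0 = 0.0343 and S1 = 0.0343. The two tails are 0.369 and 0.002, total 0.370.

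| Use, high-start vs low-start group | Crude rates | Passes screen | Passes, non-users only |
|---|---|---|---|
| 30% vs 30% | 0.210 vs 0.105 | 92% | 94% |
| 30% vs 20% | 0.210 vs 0.120 | 82% | 95% |
| 30% vs 10% | 0.210 vs 0.135 | 68% | 96% |
| 40% vs 10% | 0.180 vs 0.135 | 37% | 95% |
| 20% vs 30% (reversed) | 0.240 vs 0.105 | 98.5% | 95% |
| 10% vs 40% (reversed) | 0.270 vs 0.090 | 100% | 95% |

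The 40% vs 10% case recovers to 66% if 10% of users are counted (0.220 vs 0.145) and to 87% if 20% are (0.260 vs 0.155).

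**Step 2: a null predictor.** p = 0.20 in both groups, so 10% should pass.

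| Use | s = 0 | s = 0.20 | s = 0.40 |
|---|---|---|---|
| 30% vs 30% | 10% | 10% | 10% |
| 30% vs 20% | 16% | 10% | 14% |
| 30% vs 10% | 32% | 10% | 26% |
| 40% vs 10% | 56% | 10% | 43% |

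The distortion needs both unequal use and users counted at a rate different from non-users. Either one alone leaves the null pass rate at 10%.

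**Step 3: if baseline use is in the regression.** I simulated 40,000 studies per setting: the unadjusted screen at p<0.1, then a Mantel-Haenszel test stratified by use at p<0.05. That second threshold is my assumption, as the plan states none for the regression.

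- A null predictor (s = 0) survives both steps in about 2% to 5% of studies across the four use patterns.
- A real predictor with higher use in the high-start group can still be dropped at the screen although its adjusted test gives p<0.05:

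| Use | s = 0 | s = 0.10 | s = 0.20 |
|---|---|---|---|
| 30% vs 30% | under 1% | about 0% | about 0% |
| 30% vs 20% | 9% | about 2% | about 0% |
| 30% vs 10% | 25% | about 8% | about 1% |
| 40% vs 10% | 54% | about 21% | about 2% |

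With use reversed and s = 0, such drops are 0%.

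**Step 4: sample left if restricted.** At an assumed 30% use, 450 × 0.70 = 315 non-users. At an assumed 20% starting, 315 × 0.20 = 63 events.

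**The case against.** The strongest reply has four parts.

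*The intended question may be service-level.* The predictor objective refers to hospitalized female adolescents generally, the same population as the proportion objective, and section 6.2 covers changing as well as starting a method. A measure that counts switches is then legitimate, and starts among non-users would be only one possible target. This stands. No section says the target is non-users, so restriction to them should not be the lead remedy. It does not remove the need to say how users are coded, or the gain from separating the two groups.

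*Baseline use may already be a candidate predictor.* The survey and EHR forms (Appendices A and D) are not in the text available here and may list it. If it enters the model, false predictors are largely removed at the adjusted step. This also stands, but each other variable must first pass the unadjusted screen, so a masked real predictor can still be lost, and starts would still not be separated from switches.

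*The large figures are selected.* Masking occurs when use is higher in the group that starts more; reversed, the real predictor passes almost always. The worst figures also need users never to be counted. This is fair, and both directions and several counting rates are shown for that reason. Passing more often because of the imbalance is itself exaggeration, not protection.

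*The work is exploratory.* Section 2.2 states no hypotheses. This limits the consequence but does not make the list of predictors easier to read.

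**Conclusion.** The point holds as a cheap improvement. The predictor screen and regression for initiation state no population and make no allowance for use at enrollment, while current users are eligible and expected and their coding is unstated. Under the assumed rates, a real predictor's chance of passing the screen runs from 37% to 100% depending on how use is distributed, against 92% at equal use. A null predictor's chance rises from 10% to between 16% and 56%. The effect is modest when use differs little (30% vs 20%) and small when users are counted at about the rate of non-users. No rate comes from the documents, so the actual size is unknown.

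A reader might infer more than this, and the text does not support it:

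- That the plan prescribes the analysis in all participants, or codes a continuing user as no initiation. Both are default readings of silence.
- That 16% to 56% of null predictors would be reported as findings. Those figures describe the screen only; with use in the model, about 2% to 5% survive both steps.
- That imbalance in use always hides effects. It can equally inflate them.
- That the all-participant proportion is wrong. It matches the section 2.1 objective of counting those who "are prescribed/initiate any contraceptive during hospital admission or immediately post discharge".

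No confirmatory result is at risk. The consequence is confined to the interpretation of the predictor list.

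**What to change.** Check Appendices A and D first for an existing baseline-use item. Then, in section 17.1:

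1. Classify each participant as a current user or non-user at enrollment, from the baseline survey and EHR, with a written definition.
2. Code new start separately from switch or renewal in the derived outcome, and state how continued use is coded.
3. State the population for the predictor steps, and stratify by baseline use or force it into both the p<0.1 screen and the regression. This keeps all 450.
4. Report the non-user-only analysis as a companion, and keep the all-participant proportion as the service measure. The interest analyses under the first objective need no change.

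The cost is plan wording, one baseline variable and one recoded outcome. The harder parts are the definition of current use (condoms, lapsed methods, use for non-contraceptive reasons) and an EHR source that distinguishes a start from a renewal. Section 24.0 (Confidential Health Information, item 2.1) already foresees access to contraceptive prescription, initiation and discontinuation data. The companion analysis will have fewer events, about 63 starts among 315 non-users under the assumptions above, which limits how many predictors it can carry.

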12.0 Local Number of Subjects

- 12.1* It is expected that 450 participants will be recruited for the study.
- 12.2* It is expected that 1,000 adolescents will be eligible for the study from 2021-2023. We estimate that 45% will agree to participate.

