23.0 Resources Available

23.1 Describe the resources available to conduct the research: For example, as appropriate:

- We conservatively estimate that the demand for inpatient hospitalization will be equally present in 2021 and 2022 as it was in 2019. We estimate that at least 1000 adolescents eligible

for our study will be admitted to Nationwide Children's Hospital following units – Psychiatric Unit, Youth Crisis Stabilization Unit, Psychiatric Crisis Department Extended Observation Care Unit and Hospital Pediatrics service. We estimate that 45% will agree to participate in our study. A demonstration that at least 25% of this sample is interested in contraception care during hospitalization will be notable

- A span of 2 years will be dedicated to study recruitment. The time devoted during that span may vary based upon eligible patients per day as well as follow-up survey schedules.
- All research processes will be carried out on the unit at the time of enrollment. The only exception is verbal consent from the parent or guardian of those who are 14. In those cases, consent may be obtained verbally via telephone after receipt of the study information sheet. The follow-up surveys will be sent electronically, and subjects will complete them on their own time.
- We do not anticipate any medical or psychological distress as a result of this study; however, at the time of enrollment subjects will be admitted so they will have access to all medical and psychological services that NCH provides.
- All study staff are required to complete all research training (CITI and NCH specific human subjects training) prior to being added to the IRB. Additionally, staff will be required to undergo study specific education before involvement in study procedures. All education will be tracked on a training log. If there are any changes made to the IRB all staff will also be required to review the changes. The dates of training will be available in the study Training Log.

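### Comparing hospital initiators only with BC4Teens initiators cannot show which setting a factor acts on; a two-step analysis with an at-risk clinic denominator would

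*Combined protocol and SAP*

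**What the plan says.** All of this stands in section 17.1, under the second objective.

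- **Outcomes:** "the dependent variables are contraceptive prescription/initiation during hospitalization and contraceptive prescription/initiation following discharge".
- **Coding:** one derived variable with three levels, "Initiation any contraceptive (in hospital, in BC4Teens clinic, none".
- **Proportions:** the "proportion of participants who initiate any contraceptive in the a) hospital setting, b) in BC4Teens clinic, and c) either hospital or BC4Teens clinic". The same set is then repeated among participants interested in contraception care.
- **Comparison by setting:** a later bullet begins "To better understand personal and system-level differences in initiation of contraception during hospitalization and in BC4Teens clinic". It compares hospital initiators with clinic initiators on demographic, survey and EHR variables by chi-square. Method type (chi-square) and days from enrollment (t-test) are also compared by setting.
- **Predictors:** any initiation is related to survey and EHR variables one at a time. Those with p < 0.1 then enter a regression.

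No analysis takes participants discharged without a start as its denominator. The section does not say how someone with a start in both settings is coded.

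**The concern.** The two settings follow one another. If the three levels are exclusive, a clinic start can come only from someone not coded as a hospital start. Two separate things follow.

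1. **Depletion.** Clinic initiation over all participants falls as hospital initiation rises, even if the clinic does equally well with those who reach it unstarted.
2. **Restriction to initiators.** A comparison of hospital with clinic initiators responds to anything that changes hospital starting, clinic starting, or both. It cannot say which.

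The bullet exists to learn what drives initiation in each setting. A reader could credit or blame the clinic for a pattern that arose on the ward, or the reverse. Location of initiation is a secondary endpoint (section 4.1) and predictors of initiation are a secondary objective (section 2.1), so the reading matters.

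**Working it through.** **Inputs from the documents.** Sections 12.1 and 12.2 give N: 1,000 eligible × 0.45 = 450, which reproduces the stated sample size. This is a recruitment count, not a power calculation. The only benchmark rate is 25% in section 23.1, and it concerns interest, not initiation. No initiation rate by setting is given, so all rates below are assumptions.

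**Model.** Let h be the probability of a hospital start and c the probability of a clinic start given no hospital start. Then:

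- clinic initiation over all participants = (1−h)c
- odds of hospital versus clinic among initiators = h/[(1−h)c]
- odds ratio for a factor (1 = present, 0 = absent) = (h1/h0) × [(1−h0)c0]/[(1−h1)c1]

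**Step 1: denominator.** Take c = 20% throughout.

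| h | Clinic initiation, all 450 | At risk | Clinic initiation, at risk |
|---|---|---|---|
| 5% | 0.95 × 20% = 19% | 428 | 20% |
| 10% | 18% | 405 | 20% |
| 20% | 16% | 360 | 20% |
| 40% | 12% | 270 | 20% |
| 50% | 10% | 225 | 20% |

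**Step 2: initiator-only contrast.** Take N = 450 with the factor present in half (225 and 225). Counts are expected values, present/absent. Power is for the two-sided 0.05 comparison of the two initiator groups.

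| Factor acts on | h1/h0 | c1/c0 | Hospital starts | Clinic starts | Factor present: hospital vs clinic initiators | OR | Power |
|---|---|---|---|---|---|---|---|
| Neither | 20/20% | 20/20% | 45/45 | 36/36 | 50% vs 50% | 1.00 | – |
| Hospital only | 30/10% | 20/20% | 67.5/22.5 | 31.5/40.5 | 75% vs 44% | 3.86 | 98.5% |
| Clinic only | 20/20% | 30/10% | 45/45 | 54/18 | 50% vs 75% | 0.33 | 91% |
| Both equally | 30/10% | 30/10% | 67.5/22.5 | 47.25/20.25 | 75% vs 70% | 1.29 | about 10% |
| Both equally | 40/20% | 40/20% | 90/45 | 54/36 | 67% vs 60% | 1.33 | about 18% |
| Both equally | 60/20% | 60/20% | 135/45 | 54/36 | 75% vs 60% | 2.00 | about 71% |

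Reversing the clinic-only row (c1 = 10%, c0 = 30%) gives (0.2/0.2) × (0.8 × 0.3)/(0.8 × 0.1) = 3.00. A factor that only lowers clinic starts therefore looks much like one that only raises hospital starts (3.86).

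In the hospital-only row, clinic initiation over all participants is 0.7 × 20% = 14% with the factor and 0.9 × 20% = 18% without it. Among those at risk it is 20% in both.

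**Step 3: depletion alone.** When the factor has the same rates in both settings, h1/h0 and c1/c0 cancel and the odds ratio is (1−h0)/(1−h1): 0.9/0.7 = 1.29, 0.8/0.6 = 1.33, 0.8/0.4 = 2.00.

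**The case against.** The strongest reply is that most of the needed information is already planned.

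- **Total uptake.** The either-setting proportion and the any-initiation regression do not restrict to initiators. This stands: both are sound for total uptake, and non-initiators are not absent from the plan as a whole. They do not separate the settings, however.
- **Three-level table.** If the one-at-a-time predictor analysis keeps all three levels, hospital, clinic and none appear side by side for each categorical variable. The at-risk rate then follows by division, for example 18%/(100% − 10%) = 20%. This stands in part. It needs exclusive coding, which the plan does not state, and it gives nothing for continuous predictors or adjusted models. The two-group t-test for continuous predictors also suggests a yes/no outcome.
- **Descriptive proportion.** Clinic initiation over all participants is a legitimate measure of what each setting contributes. This stands. That it falls as hospital uptake rises is a property of the measure, not an error.
- **Real differences.** If hospital initiation truly differs by a factor, the initiator contrast reflects something real. This stands, but the contrast still does not say where the factor acts.

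A reader might go further and infer that conditioning on initiation creates the differences between settings, or that the clinic can start only those who left without a method. The documents support neither. A factor unrelated to starting gives an odds ratio of 1.00. The second claim is an inference from the coding. Section 6.2 allows for participants who want to change methods, and section 17.1 tracks preferred and non-preferred starts separately, so a hospital start followed by a clinic start is not excluded.

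**Conclusion.** The concern holds in a limited form. The initiator-only comparison mixes the chance of a hospital start with the chance of a clinic start among those not started. It cannot show which setting a factor affects, and its result may be distorted or partly produced by depletion.

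Under the assumed rates, single-setting effects give odds ratios of 3.86 (hospital only) and 0.33 (clinic only). Depletion alone gives about 1.3 at low to moderate uptake, which the test would rarely detect, and 2.00 at high uptake. These figures rest on exclusive three-level coding, clinic starts following discharge, a factor present in half of 450 participants, and illustrative rates that the documents neither give nor rule out.

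The proportions planned for the second objective are not invalidated. This is an inexpensive improvement to an exploratory comparison in a study that states no hypotheses (section 2.2).

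**What to change.** In section 17.1:

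1. Keep the all-participant and interested-participant proportions and call them descriptive.
2. Add clinic initiation among those discharged without a start.
3. Analyse predictors in two steps with non-initiators included: (a) hospital start, yes or no, among all and among interested participants; (b) clinic start, yes or no, among those discharged without a start.
4. State how a participant with a start in both settings is coded.
5. Label the comparison of hospital with clinic initiators descriptive.

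No new data are needed; only the text of a few bullets changes. The cost is a smaller denominator at the clinic step. With h = 20% it is 450 × 0.8 = 360. If, for illustration, only the 25% benchmark were interested, the interested group would be 450 × 0.25, about 112, of whom about 112 × 0.8 = 90 would remain, so step (b) could carry few predictors there. Those discharged without a start are also a selected group, since some may have declined. Results of step (b) should be described as applying to that group only.
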